Title of Study: The Live Long Walk Strong Rehabilitation Program: What Features Improve Mobility Skills?

NCT 04026503

8.8.2019

Primary Outcome: The primary outcome for all aims of this study is usual Gait Speed.^{53,54} Gait speed is recorded by stopwatch over a 4-meter walking course beginning from a standing start. The fastest of 2 trials is recorded in meters/seconds. Declining gait speed is associated with heightened risk for adverse health outcomes (hospitalization, disability, death) over 1-4 years of subsequent follow up.^{53,54} Changes in gait speed of .05 and 1.0m/s are characterized as small and large clinically meaningful differences respectively.^{24,55} For Aims 2 & 3, we will identify factors that mediate changes in gait speed. Our experience with LLWS and related clinical trials identifies that the majority of participants (> 70%) exceed a .09 m/s change after treatment.]

Timing and coordination of gait

Smoothness of walking is our primary measure of timing and coordination and is an integrated measure of motor control of walking.^{37,56} It is assessed during usual over ground walking. Linear acceleration of the body is measured along three axes (vertical, anterior-posterior and medial-lateral) using a tri-axial accelerometer attached to the skin over the lumbar spine (L3 segment). Trunk accelerations are sampled at 200 Hz and used to calculate the harmonic ratio following the methodology of Menz.^{37,56} The harmonic ratio is derived in the vertical, medial-lateral and anterior-posterior directions. Higher harmonic ratios indicate greater levels of functioning. Our prior work reports mean changes of 25-30% in smoothness of walking occur with training.¹⁸

Gait variability will be a secondary outcome and is defined as fluctuations in gait characteristics from one step to the next.⁵⁷ It is an indicator of impaired mobility in older adults⁴⁰ and will serve as a secondary indicator of timing and coordination. Gait variability is quantified using established measures of temporal and spatial gait characteristics including stance time, step length, and step width. Variability will be calculated as the standard deviation of the set of steps recorded over 4 passes on the ZenoMat, an instrumented walkway. Approximately 32 steps will be collected from 4 passes on the ZenoMat which will be more than adequate to achieve a stable measure of gait variability. Our prior work has shown that 20 steps are sufficient to achieve a reliability of 0.75 and 30 are sufficient for 0.80.^{40,58} In general, lower variability is better.

Leg Power, Leg strength and Leg Velocity will be measured separately for each leg by determining a 1 repetition maximum (1RM) from 6 to 12 trials on a leg press machine (Keiser Pneumatic Leg Press; Fresno, CA). Leg muscle power is measured separately on each leg using the same equipment. Five repetitions will be performed at 40% and 70% 1RM. The highest value of the repetitions will be recorded. Peak leg velocity is derived from power recorded at 40% of the 1RM, by the formula $Velocity = power / 0.4(1RM)$. The test-retest reliability of these measures is excellent ($r > .85$).^{42,59,60} Leg power will be our primary outcome measure whereas leg strength and leg velocity will be secondary outcomes. A 9-10% change in leg power is clinically meaningful and our proposed treatment approach can exceed that threshold (see study 3, preliminary work).⁶¹

Trunk Extensor Muscle Endurance is measured using a technique that is reliable and valid among community dwelling older adults.³¹ This is measured while the participant is lying prone on a specialized plinth positioned 45 degrees from vertical. Subject's feet are supported on a footplate and fixed in position. A portion of the table that is hinged and positioned at waist level is lowered to the horizontal plane and subject is asked to maintain their position as long as possible with their arms across his chest. The test is terminated when the subject can no longer maintain the unsupported position or after 150 seconds. Time is recorded in seconds and only one trial is performed. Reliability for the trunk measure is excellent ($r = .88-91$).³¹ We have observed mean changes of 48% with LLWS (see study 3, preliminary work).

Self-Efficacy Scale for Exercise is an established, reliable and valid scale measuring an individual's confidence to engage in exercise.^{45,62} It is sensitive to change and successfully utilized within studies of older adults with mobility problems, including our previous RCT among hip fracture patients.^{45,62}

Secondary Outcome Measures: [The SPPB total score will be a secondary outcome for each aim. The SPPB is a well-established, valid and reliable physical performance measure used extensively in aging research. It is a composite measure of three functional tasks: usual gait speed over 4 meters from a standing start, 5 times repeated chair stand, and progressive standing balance. Each task is scored between 0-4 (higher score corresponds to better performance), with a maximum summary score of 12. Each increment decline in SPPB total score is associated with heightened risk for adverse health outcomes.^{53,54} Changes in SPPB of 0.5 units and 1.0 units are characterized as a small and large clinically meaningful differences respectively.^{24,55} The Late Life Function and Disability Instrument (LLFDI) will also be a secondary mobility outcome. The LLFDI is a reliable patient-reported (by interview or phone) measure of functional mobility validated in a wide range of older adult populations, having been used in over 70 clinical trials worldwide.⁶³ We have previously reported that LLFDI-Function and its sub domains are very sensitive to change.³⁵ Scores for all domains are scaled between 0-100 and clinically important differences are defined.]⁶⁴

Covariates & potential confounding variables: Clinical characteristics including age, gender, educational attainment, race, and marital status will be recorded. Height and weight will be measured using standardized methods and body mass index (BMI) will be calculated as weight (kg) divided by height in squared meters.⁶⁵ Comorbidity will be measured using a valid and reliable questionnaire that allows for the characterization of whether these conditions require treatment or impact physical function.⁶⁶ Depression will be measured by the 10-item Center for Epidemiologic Studies-Depression Scale (CES-D),^{67,68} a widely used screening tool for symptoms of depression that discriminates well between general population samples. The Brief Pain Inventory questionnaire will measure pain.^{69,70} Falls, fall related injuries and illnesses will be recorded via monthly calendars.⁷¹ Also, we will administer the Activities-specific Balance Confidence (ABC) Scale, which is a well-established and validated scale measuring confidence with balance and mobility.^{62,72} Given the strong association between mobility skills and cognition, participants will also undergo the NIH toolbox cognition battery.⁷³ Knee and ankle range of motion will be measured using a goniometer. Maximal knee flexion and extension are measured in degrees, while the ankle range of motion is measured as a binary measure for both dorsiflexion (ability or inability to dorsiflex to 90 degrees) and plantarflexion (ability or inability to plantarflex 20 degrees). Reliability for this measure is excellent (r=.82-.98).⁷⁴ [Every 4 weeks of study participation, we will assess physical activity and exercise engagement among all participants. Physical activity will be measured via the Phone-Fitt,⁹ a measure ascertainable by phone or in person that is validated against actigraphy measures. Exercise engagement will be measured by self-report as specified in section 3.G.vi.]

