Live Long Walk Strong SAP

NCT 04026503

8.8.2019

Initially, we will view plots and calculate simple descriptive statistics for all continuous measures, and frequencies and percentages for all categorical variables to examine the data distributions and check for data accuracy and completeness.

Derived variables (change from the baseline to each follow-up visit as well as change between consecutive visits and time intervals between visits) will be calculated and examined.

Two sample t-test will compare mean scores in changes of gait speed (Δ GS) and LLWS target attributes (ATTR) between treatment and control groups at baseline and a t-test for paired samples will evaluate changes between follow-up visits.

Multiple regression models will assess relationships between dependent and independent variables and causal mediation models will be used for mediation analysis. Mixed effects regression models will be used to analyze repeated measures. In regression and mediation models, we will examine and adjust for potential confounding factors (by design or as covariates), including baseline scores (as appropriate), age, sex, BMI, comorbidity-score, etc.

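### Does the printed 1.0 m/s for a large meaningful change in gait speed put the primary outcome at risk?

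*Protocol*

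**What the plan says.** The Protocol's Primary Outcome section fixes the endpoint: "The primary outcome for all aims of this study is usual Gait Speed". It describes the measurement: "Gait speed is recorded by stopwatch over a 4-meter walking course beginning from a standing start". It then gives two benchmarks, citing references 24 and 55: "Changes in gait speed of .05 and 1.0m/s are characterized as small and large clinically meaningful differences respectively". The paragraph ends with the team's own experience, that "the majority of participants (> 70%) exceed a .09 m/s change after treatment".

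The Secondary Outcome Measures section has a parallel sentence with the same two citations: "Changes in SPPB of 0.5 units and 1.0 units are characterized as a small and large clinically meaningful differences respectively".

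The SAP's statement on the primary outcome is "Two sample t-test will compare mean scores in changes of gait speed", with the target attributes of the program handled the same way. Regression, mixed-effects and mediation models follow. Neither benchmark appears in the SAP.

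**The concern.** A large threshold of 1.0 m/s sits badly beside the other figures in its own paragraph. A gain of that size in usual walking pace over 4 m would roughly double or more than double the speed of most older adults with mobility problems. The same sentence pattern for the SPPB has a large value only twice the small one.

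Gait speed is the primary outcome for every aim, and this sentence is the only place where the documents say what size of change counts as large. A reader who took 1.0 m/s literally would place every plausible result below large. A responder analysis at that cut-off would find almost no treated responders. A later report using a smaller cut-off might also look as if it had moved the threshold after seeing the data.

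**Working it through.** The documents contain no sample size, power, SD or baseline speed, so there is no planned calculation to reproduce. The check has two parts: whether the figure is credible, and whether anything uses it.

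**Inputs from the documents.** Gait-speed thresholds of 0.05 and 1.0 m/s, and more than 70% of participants above 0.09 m/s after treatment (Protocol, Primary Outcome). SPPB thresholds of 0.5 and 1.0 units (Protocol, Secondary Outcome Measures).

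**Ratios.**
- Gait speed, large to small: 1.0 / 0.05 = 20.
- SPPB, large to small: 1.0 / 0.5 = 2.
- Printed large value against the team's figure: 1.0 / 0.09 = 11.1.
- SPPB ratio applied to the small gait-speed value: 2 × 0.05 = 0.10 m/s. The printed value is 1.0 / 0.10 = 10 times that.

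**What a 1.0 m/s gain would require.** Time over 4 m is 4 / speed. Baselines are assumed.

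| Baseline (m/s) | Time before (s) | Speed after (m/s) | Time after (s) | Gain in speed |
|---|---|---|---|---|
| 0.4 | 10.0 | 1.4 | 2.86 | 250% |
| 0.8 | 5.0 | 1.8 | 2.22 | 125% |
| 1.2 | 3.33 | 2.2 | 1.82 | 83% |

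**How often a treated participant would exceed 1.0 m/s.** Assume normally distributed changes with exactly 70% above 0.09 m/s. Then mean = 0.09 + 0.524 × SD, and P(change > 1.0) = 1 − Φ((1.0 − mean) / SD). SDs are assumed.

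| SD (m/s) | Mean change (m/s) | P(> 1.0) | P(> 0.10) |
|---|---|---|---|
| 0.10 | 0.142 | < 0.00001 | 0.66 |
| 0.15 | 0.169 | 0.00000001 | 0.68 |
| 0.20 | 0.195 | 0.00003 | 0.68 |
| 0.25 | 0.221 | 0.0009 | 0.69 |
| 0.30 | 0.247 | 0.006 | 0.69 |

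A mean change of 1.0 m/s would need an SD of (1.0 − 0.09) / 0.524 ≈ 1.74 m/s. The printed value is therefore not credible as a threshold for this outcome.

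**Where the figure is used.** Each place where a threshold could act was checked in both documents:
- Sample size or power: none is posted.
- Responder definition or cut-point for gait speed: none.
- Success criterion or margin: none.
- Tests and models: t-tests on mean changes, then regression, mixed-effects and mediation models. None takes a clinical threshold as input.

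Replacing 1.0 with any other number leaves every planned estimate, interval and p-value unchanged.

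**What remains for interpretation.** The 0.05 m/s value is not in dispute. The modelled mean changes run from 0.142 / 0.05 = 2.8 to 0.247 / 0.05 = 4.9 times that value, so it still separates a meaningful result from a trivial one. These are changes after treatment, not differences between arms; the documents give no control-arm change.

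**The case for a change.** The strongest case for acting is that a posted protocol is the text against which later claims are checked. The error is about tenfold, it concerns the primary outcome of all aims, and correcting it costs one number and a look at two sources already cited. All of that is true, and the figure is very probably wrong.

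The argument weakens at the step from a wrong number to harm:
- No responder analysis is planned, so a responder rate near zero describes an analysis that the trial does not propose.
- Understating a large effect as small assumes a reporting rule that neither document contains.
- The 0.09 m/s remark does not require a large threshold near 0.10. It reads equally well as saying that most participants pass the small threshold of 0.05.
- Shared citations do not oblige a 0 to 12 composite score and a speed in m/s to have the same large-to-small ratio.
- The claim that no achievable result could be large rests on assumed baselines and SDs. Having more than 70% above 0.09 m/s sets no upper limit on change.

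What stands is that the sentence contains a probable transcription error, and that a reader who wants to use the word large should go to references 24 and 55 for the value.

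**Conclusion.** The concern is right about the number and wrong about its consequences. The printed 1.0 m/s is 10 to 11 times what the documents' other figures suggest, most likely through a misplaced decimal or a carry-over from the SPPB value; the documents do not show which. The effect on the planned analysis is nil, because no test, model, sample size or decision rule in the posted documents takes the figure as input. The effect on interpretation is confined to one adjective, with the 0.05 m/s benchmark intact.

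This is a clerical slip in descriptive background, and an analyst would notice it at once from the neighbouring figures. No change to the plan is needed. The conclusion rests on the posted text: the Protocol refers to sections and preliminary work that are not included, and a use of 1.0 m/s there as a design input would have to be judged separately. A value near 0.10 m/s is only an inference and should not be treated as the documents' own threshold.

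### Does the 150-second stop on the trunk endurance test need its own analysis rule in the SAP?

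*Protocol*

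**What the plan says.** In the protocol paragraph on Trunk Extensor Muscle Endurance, the "subject is asked to maintain their position as long as possible", and "The test is terminated when the subject can no longer maintain the unsupported position or after 150 seconds". The score is simple: "Time is recorded in seconds and only one trial is performed". The protocol describes the test as "measured using a technique that is reliable and valid among community dwelling older adults" and cites earlier experience: "We have observed mean changes of 48% with LLWS". It gives no baseline mean, SD or share of participants at the limit.

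Under Primary Outcome, the protocol names gait speed for all aims and adds: "For Aims 2 & 3, we will identify factors that mediate changes in gait speed".

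The SAP compares changes in gait speed and in the target attributes between arms by t-test. It uses multiple regression and mixed models, and states that "causal mediation models will be used for mediation analysis". Before any of this, it plots and summarises every continuous measure to examine its distribution. It does not list the target attributes by name, and it has no rule for values at 150 s.

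**The concern.** A participant told to hold as long as possible and stopped at 150 s has a hold time of at least 150 s, not exactly 150 s. The planned models would take 150 as the exact time. If treatment moves more people to the limit than control does, part of the gain goes unrecorded and the arm difference in seconds is too small as a measure of how much hold time improved.

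The stake is in Aims 2 and 3. If trunk endurance is one of the mediators tested (a fair inference, but not stated), a weak indirect effect could reflect the ceiling rather than the biology. The SAP also names no output giving the number of participants at 150 s.

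**Working it through.** **Inputs from the documents.** Limit 150 s, one trial, time in seconds, and an earlier mean change of 48%, all from the trunk endurance paragraph. There is no planned figure to reproduce: neither document gives a sample size, a control-arm gain, or a mean or SD for hold time. Everything else below is assumed.

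**1. Direction.** With S(t) the proportion still holding at time t, the mean recorded time is the integral of S(t) from 0 to 150. If the arms are alike at baseline, then

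uncapped difference − recorded difference = integral of [S_treated(t) − S_control(t)] from 150 upward.

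This cannot be negative if treatment lengthens hold time, so the direction is as feared.

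**2. Size.** Two sets of assumptions were used.

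- Set A: gamma and log-normal times, coefficient of variation 0.4 to 0.8, treated mean 1.48 times the control mean, no change in controls.
- Set B: log-normal times, gains of 48% treated and 15% control, baseline SD 25, 35, 40 and 45 s in row order, residual log SD 0.25, difference in change scores.

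| Baseline mean | Treated at 150 s, A | Difference kept, A | Treated at 150 s, B | Difference kept, B |
|---|---|---|---|---|
| 40 s | 0.2–5.3% | 89–100% | 4% | 91% |
| 60 s | 5.9–16.5% | 71–95% | 12% | 78% |
| 80 s | 21.0–28.4% | 54–81% | 24% | 65% |
| 100 s | 35.5–43.4% | 41–62% | 39% | 51% |

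One worked line from Set A (gamma, coefficient of variation 0.6, mean 80 s): the uncapped difference is 0.48 × 80 = 38.4 s, the recorded difference is 25.0 s, and 25.0/38.4 = 65%. At Set B means of 20 and 30 s, 99% and 97% are kept.

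**3. Can the 48% locate the trial in this table?** If it is a change in mean recorded time, the follow-up mean cannot exceed 150 s, so the recorded baseline mean is at most 150/1.48 = 101 s. No row is excluded.

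**4. Mediation.** Ratio of the estimated to the true indirect effect under Set B, when gait speed keeps rising with seconds held beyond 150 s:

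| Mediator form | 40 s | 60 s | 80 s | 100 s |
|---|---|---|---|---|
| Change, baseline-adjusted | 0.89 | 0.75 | 0.63 | 0.52 |
| Follow-up value, unadjusted | 1.02 | 0.98 | 0.91 | 0.81 |

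In the second form the treatment-to-mediator path shrinks, but the mediator-to-gait slope rises and offsets part of the loss. The SAP fixes neither form and adjusts for baseline only where appropriate, so neither row is the effect of the plan as written. If the benefit to gait stops at 150 s, the first form gives 1.00 throughout.

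**5. Standardised difference.** The cap shrinks the SD as well as the difference. Under Set B the standardised difference goes from 0.79 to 0.85 at 80 s and from 0.82 to 0.80 at 100 s. Under normal times with proportional gains it fell from 0.93 to 0.73 at 80 s and to 0.53 at 100 s. Any effect on the power of this comparison therefore depends on the assumed distribution.

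**6. What a censored analysis would add.** A joint log-normal model treating 150 s as right-censored, at a baseline mean of 100 s with trials of 200 participants (assumed), gave 0.85 of the true indirect effect when benefit continues in seconds and 1.17 when it stops at 150 s. The baseline-adjusted capped analysis gave 0.51 and 1.00 in the same two cases.

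**The case for a change.** The best case for a change is that the direction is certain, the remedy needs no new data, and the protocol's own 48% says treated participants will move toward the limit. For the arm difference, censored regression does recover the uncapped value when its distribution is right: a Tobit fit to normal times returned 38.2 s against a true 38.4 s, where the raw difference in recorded follow-up times was 33.8 s. If benefit continues in seconds past 150 s and the ceiling is heavy, the joint model is also closer than the capped analysis (0.85 against 0.51). And without a count at 150 s, a reader of the results cannot separate a weak mediator from a ceiling.

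The arithmetic stands, and so does the value of the count. The need for a new rule does not. A 48% gain says how far people move, not where they start, so it does not show that the limit is reached. The understatement exists only against unlimited hold time, a quantity neither document sets out to estimate. The censored model depends on a distribution beyond 150 s and on an untestable view of benefit there; where benefit stops at 150 s it overstates an effect that the capped analysis gets right. Even its advocate would keep the planned analysis as primary and let the extra run decide nothing.

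**Conclusion.** No change to the plan follows. A fixed stopping time is part of the test as the protocol defines it, and the planned analyses are valid for the resulting score, hold time up to 150 s. Read that way, the arm difference is not biased.

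The gap to uncapped hold time could be nil or could be about half the difference: roughly 0% to 11% lost at a baseline mean of 40 s and 38% to 59% at 100 s. These figures rest on assumed means, SDs and distribution shapes, and the documents contain nothing that picks out a row. The loss in an indirect effect needs four further things: trunk endurance being a mediator, many treated participants at the limit, benefit continuing past 150 s, and a mediation form that does not offset the shrinkage.

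What remains is a gap that analysts fill sensibly. The planned plots and summaries will show any pile-up at 150 s. An analyst who sees one would naturally describe the outcome as time up to 150 s, give the counts by arm and visit, and consider a censored analysis only if those counts are material. Gait speed, the primary outcome, is not affected.

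### Could the open covariate list lead the treatment-effect models to adjust for activity, engagement, falls or illness recorded during follow-up?

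*Protocol*

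**What the plan says.** The Protocol section on covariates and potential confounders opens with fixed traits: "Covariates & potential confounding variables: Clinical characteristics including age, gender, educational attainment, race, and marital status will be recorded". The same paragraph goes on to measures of other kinds. For pain: "The Brief Pain Inventory questionnaire will measure pain". For balance confidence: "Also, we will administer the Activities-specific Balance Confidence (ABC) Scale". For events over time: "Falls, fall related injuries and illnesses will be recorded via monthly calendars". It closes with activity and engagement: "Every 4 weeks of study participation, we will assess physical activity and exercise engagement among all participants". Engagement is defined elsewhere: "Exercise engagement will be measured by self-report as specified in section 3.G.vi", a section that is not in the public text.

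The last paragraph of the SAP says: "In regression and mediation models, we will examine and adjust for potential confounding factors (by design or as covariates"). The factors follow: "including baseline scores (as appropriate), age, sex, BMI, comorbidity-score, etc". The word baseline is attached only to scores. The same paragraph assigns multiple regression to relating dependent to independent variables, causal mediation models to the mediation analysis, and mixed models to repeated measures. The paragraph before it gives a two-sample t-test for the group comparison of changes in gait speed and in the target attributes.

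**The concern.** The SAP's phrase for what it will adjust for closely matches the Protocol's heading, so a reader may take everything under that heading as the pool of candidates. Four-weekly activity and engagement, and monthly falls and illness, are in that pool, and nothing in the SAP shuts them out.

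An exercise programme may well change activity and engagement. If such a measure enters a model meant to estimate the effect of treatment on gait speed, the treatment coefficient no longer estimates the total effect. The part of the effect that runs through the measure is removed, and any unmeasured cause shared by the measure and gait speed brings in further bias. Gait speed is the primary outcome for all aims, so a real misstep here would matter. In the mediation analysis of Aims 2 and 3, a treatment-affected measure of this kind could also distort the indirect effect, depending on which models it enters.

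**Working it through.** **What the texts commit to.** No stated figure exists to reproduce, so the texts come first.

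- The Protocol paragraph says what will be collected and how. It does not say that any item enters a model.
- The SAP names baseline scores, age, sex, BMI and comorbidity score. It names none of activity, engagement, falls, injuries or illness. After a run of baseline-type items, *etc.* most naturally means more of the same.
- The SAP adjusts for confounders. A consequence of treatment is not a confounder of the treatment effect.
- The t-test carries no covariates and cannot be affected.
- Neither the multiple regression nor the mixed model is described as the source of the treatment-effect estimate. In a regression of gait change on attribute change, follow-up illness or activity might be a proper adjustment.

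**Size if the misstep were made.** In a linear model with arm and one covariate,

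unadjusted effect − adjusted effect = *a* × *s*,

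where *a* is the between-arm difference in the covariate (SD) and *s* is the within-arm slope of gait speed on it (m/s per SD). Both are assumed; the documents give neither.

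| *a* | *s* = 0.01 | *s* = 0.03 | *s* = 0.05 |
|---|---|---|---|
| 0 | 0 | 0 | 0 |
| 0.2 | 0.002 | 0.006 | 0.010 |
| 0.5 | 0.005 | 0.015 | 0.025 |
| 0.8 | 0.008 | 0.024 | 0.040 |

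The largest entry is 0.040 / 0.05 = 80% of the Protocol's small meaningful difference (Primary Outcome paragraph). The shift is zero whenever *a* = 0 or *s* = 0.

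A simulation of 2,000,000 records agrees. Its assumptions were a total effect of 0.05 m/s, a covariate shifted by 0.5 SD, and a residual SD of 0.12 m/s. With no shared cause, the adjusted effect is 0.050, 0.045, 0.038 and 0.025 when the covariate carries 0%, 10%, 25% and 50% of the effect. With an unmeasured shared cause (0.03 m/s per SD on gait speed, correlation 0.5 with the covariate within arm) it is 0.042, 0.038, 0.030 and 0.017. The last value follows from the formula: *s* = 0.05 + 0.03 × 0.5 = 0.065, the shift is 0.5 × 0.065 = 0.0325, and 0.05 − 0.0325 = 0.0175.

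**Mediation.** Assumed paths: treatment to mediator 0.3, mediator to gait speed 0.05, direct effect 0.03. Engagement is affected by treatment and affects both mediator and gait speed. The true indirect effect is (0.3 + treatment→engagement × engagement→mediator) × 0.05. The estimates come from simulations of 1,000,000 records.

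| Treatment→engagement, engagement→mediator, engagement→gait | True | In neither model | Outcome model only | Both models |
|---|---|---|---|---|
| 0.8, 0.3, 0.02 | 0.0270 | 0.0303 | 0.0273 | 0.0152 |
| 0.8, 0.3, 0.04 | 0.0270 | 0.0329 | 0.0270 | 0.0150 |
| 0.5, 0.3, 0.02 | 0.0225 | 0.0252 | 0.0227 | 0.0151 |
| 1.2, 0.4, 0.04 | 0.0390 | 0.0497 | 0.0389 | 0.0149 |

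Baseline-only adjustment (the column for neither model) overstates in every row: 0.0303 / 0.0270 = 1.12, 0.0329 / 0.0270 = 1.22, 0.0252 / 0.0225 = 1.12, 0.0497 / 0.0390 = 1.27, that is 12% to 27%. Entering engagement in both models understates. A blanket ban on follow-up covariates would therefore not repair the mediation analysis.

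**The case for a change.** The strongest case for a change is that it costs only wording. A closed list of pre-treatment covariates would record the intent if the authors already mean that, and prevent a biased estimate if they do not. It would also stop covariates being chosen after results are seen, which a promise to examine and adjust, with an open list, leaves possible. An analyst who adjusted for four-weekly engagement could claim to be within the plan.

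Much of this stands. The list is open, the follow-up items do sit under that heading, and a closed list would be tidier. What does not stand is the step from an open list to a fault in the plan. The misuse needs the analyst to read *etc.* against the items that precede it and to call a consequence of treatment a confounder. It also needs a regression or mixed model to be made the treatment-effect estimate, which the SAP does not say. The engagement section that might settle the role of that measure is not public.

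The lack of time points for pain, depression and balance confidence adds little, because the public extract gives no visit schedule for those or the other assessments.

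**Conclusion.** No change is called for. The observation about the text is accurate, but it describes missing detail that sensible analysts fill with baseline values, and no planned error is shown. The one between-group comparison the SAP spells out is untouched.

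The possible shift of 0 to 0.040 m/s rests wholly on assumed arm differences (0 to 0.8 SD) and slopes (0.01 to 0.05 m/s per SD). The 80% figure is the extreme corner of that grid. It illustrates the mechanism and says nothing about how likely the misstep is in this trial. For the mediation models, the handling of a confounder that treatment affects is a trade-off: under the assumed paths, leaving it out of both models overstates the indirect effect by 12% to 27%, and putting it in both gives about 0.015 against true values of 0.0225 to 0.0390. A simple baseline-only rule would bring no clear gain there.

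This conclusion would change if the unpublished sections, or a later analysis plan, named follow-up activity or engagement as a covariate in a model of the treatment effect.
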